According to the Montefiore standard of care, to prepare patients for surgery, the perioperative team contact patients within 1-3 days before the surgery. During this phone call, patients are given all the instructions regarding the surgical preparation, and the operative team makes sure all the needed medical records are in place. During this phone call, patients will be specifically asked about suboxone use, and an email will be sent to the research team to inform the details of the suboxone patients. The research team will screen the patients and those patients fulfilling the inclusion-exclusion criteria will be called on the day before surgery for their interest in participating in a research study. Interested patients will be provided with the study details, and all their questions will be answered. The signing of the consents will take place on the day of the surgery, an investigator associated with the study will be responsible for obtaining the informed consents.

In terms of surgery and anesthesia, the routine standard of care practiced in our hospital will be maintained for all the subjects enrolled in the study. During the study period, all the intraoperative and postoperative patient pain management guidelines will be standardized. According to the standard of practice in our institution, induction of anesthesia will take place. After induction of anesthesia, instead of intra-op and post-op Fentanyl 50mcg as needed, the patients will receive sublingual sufentanil (Dsuvia) intra-op and post-op. Detailed sublingual sufentanil is described in the next paragraph. Patients will be discharged home based on the discharge criteria followed at our institution. One of the research associates will call the patient 24 hours after discharge from the PACU to collect the information regarding their post-discharge opioid use, current pain score, adverse events, and information regarding the ED visits.

Study Objective Assessments

A research associate will be collecting the data prospectively and from the medical records. All the assessments will be coordinated with the standard of care administered at our hospital.

Study Medication and Storage

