The sponsor of the study is responsible for providing the study medication. The patient or the insurance will not be billed for the study medication. Study medication will be stored in the research pharmacy at Hutch. All appropriate storage instructions will be followed, and the pharmacist will be responsible for the drug audit. On the day of surgery for an enrolled subject, research personnel will retrieve medication from the pharmacy and deliver it to the physician for administration to subjects.

Sublingual sufentanil (Dsuvia) Study Protocol Pain Medications:

Pre-op:

Acetaminophen 975mg PO

Intra-op for induction (doses as per standard):

IV Midazolam

IV Fentanyl

IV Lidocaine

IV Propofol

After induction and before incision

Ketamine .35-.5 mg/kg IV

Dsuvia 30mcg SL (1st dose)

Postop:

If pain < or = 4/10,

Give no additional medications

If pain > 4/10

give Dsuvia 30mcg SL (2nd dose)

if 30 minutes after Dsuvia 2nd dose & pain is >4/10

give Ibuprofen 800mg IV

if 60 minutes after Dsuvia 2nd dose & pain is >7/10

give hydromorphone 0.4 mg IV

Interim Analysis

We are planning to conduct an interim analysis to evaluate the use of a single dose of Dsuvia in the intraoperative period. For this purpose, if 8 of the first 15 patients require a second dose of Dsuvia in the PACU, then the protocol will be changed to give the 2nd dose of Dsuvia in the OR at 15 minutes (or more) before extubating (and more than 1 hour since the 1st dose). The rest of the protocol will stay the same.

Comparison group

The comparison group in this study will be randomly selected from a cohort of the patients satisfying inclusion and exclusion criteria. The time frame for the comparison group will be the first Dsuvia patient to the last Dsuvia patient. For the comparison group, all the data points will be collected retrospectively. For comparison, group data points after the discharge from the hospital will not be collected. We are requesting a waiver of consent and HIPAA authorization for the comparison group as this will be

conducted retrospectively. A waiver will be needed because subjects may not be possible due to reasons such as relocation, wrong contract information given, or are no longer being seen at our institution.

Statistical analysis

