We are conducting this study as a pilot study. This pilot study's sample size is calculated based on the assumption that approximately 70% of the patients receive at least one dose of rescue opioid in the PACU. As this drug's efficacy in reducing the rescue opioids used in the PACU in this population is not studied previously, we plan to use a 50% rate reduction for calculating the sample size in this pilot study. According to our calculation estimate, we need to study 30 patients (alpha=0.05 and 1-Beta=0.85) in each group. The study will not be powered for secondary outcomes.

Descriptive statistics will be used to report all baseline demographic and clinical characteristics such as (age, gender, type of surgery, medications, ASA status, comorbidities). The primary endpoint amount of opioids used in the perioperative period will be compared using Wilcoxon rank-sum tests, and categorical variables such as adverse events and the number of patients requiring additional opioids will be analyzed using chi-square analysis or Fisher's exact tests. All the analysis will be two-tailed, and a p-value of <0.05 is considered statistically significant.

Data Management

All study data will be collected and entered into the computer database. Each subject will be assigned to a random number code, and the key linking the code and the subject identifier will be stored in a locked cabinet. The computer database will be password protected and will be kept on the HIPAA compliant Montefiore drive. The research manager is responsible for auditing the consistency of the data transcribed from the paper CRF to the computer. A protocol violation log will be maintained, and all protocol violations will be reported to the IRB and DSMB. The planned interim analysis (halfway through the recruitment) will be mainly focused on the additional dose of opioids in the PACU rather than the efficacy of the NMB reversal.

DSMB

The data safety monitoring board will be comprised of an anesthesiologist and a surgeon. All unanticipated serious adverse events will be reported to the DSMB. In the event of unanticipated serious adverse events, the continuation of the study will be at the discretion of DSMB and IRB. Periodic DSMB meetings will evaluate the occurrence of any study-related adverse events.

Human Safety

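### Drawing a random 30 chart comparators, rather than taking every eligible non-Dsuvia patient in the window, gives up precision whenever more than 30 exist, and no shortfall rule is stated

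*Combined protocol and SAP*

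**What the plan says.** The Comparison group section states: "The comparison group in this study will be randomly selected from a cohort of the patients satisfying inclusion and exclusion criteria". It confines them to the enrolment period: "The time frame for the comparison group will be the first Dsuvia patient to the last Dsuvia patient". It adds: "For the comparison group, all the data points will be collected retrospectively". A waiver of consent and HIPAA authorization is requested for these patients, and nothing after hospital discharge is collected on them.

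The Statistical analysis section gives the size: "we need to study 30 patients (alpha=0.05 and 1-Beta=0.85) in each group". This rests on the assumption that "approximately 70% of the patients receive at least one dose of rescue opioid in the PACU" and on the statement that "we plan to use a 50% rate reduction for calculating the sample size in this pilot study". The same section allows chi-square or Fisher's exact tests for categorical variables, and the Wilcoxon rank-sum test for the primary endpoint (perioperative opioid amount). It also says: "All the analysis will be two-tailed, and a p-value of <0.05 is considered statistically significant".

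On recruitment, the Informed Consent section says that patients are asked about Suboxone during the routine pre-operative call, that the research team screens them, and that "those patients fulfilling the inclusion-exclusion criteria will be called on the day before surgery" to ask about taking part.

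The document gives no count of eligible surgical patients and no expected uptake. It has no rule for using more than 30 comparators and none for finding fewer. The Introduction's figure of well over 1000 Suboxone patients in the system is not a count of eligible ambulatory operations.

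**The concern.** The scarce resource here is the Dsuvia patient, who must be consented, given study drug and telephoned. A comparator costs only chart abstraction. Equal allocation is efficient when both groups cost about the same, and here they do not. A random subset of the eligible non-participants carries the same confounding as the full set, so sampling protects against nothing and leaves a wider interval.

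This matters because 30 v 30 does not deliver the plan's stated 85% power on its own sizing assumptions. Additional concurrent comparators, if they exist, could make up the difference without exposing one more patient to Dsuvia.

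There is also a possible problem in the other direction. Dsuvia patients and comparators are drawn from the same people over the same period, so each patient who enrols leaves the comparator pool. The plan does not say what happens if fewer than 30 remain. A remedy chosen after the charts have been read would be a data-dependent choice.

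**Working it through.** **Inputs.** All from the Statistical analysis section: control rescue rate 0.70; a 50% reduction, read as relative, so 0.35 on Dsuvia; two-sided alpha 0.05; power 0.85; 30 per group. The number of comparators, m, and the uptake, f, are not in the document and are varied as assumptions.

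**Step 1: the plan's own figure.** With equal groups and pooled variance, the mean rate is 0.525 and

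n = [1.960 × √(2 × 0.525 × 0.475) + 1.036 × √(0.35 × 0.65 + 0.70 × 0.30)]² / 0.35²
= (1.384 + 0.686)² / 0.1225 ≈ 35 per group.

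The stated 30 is not reproduced. The unpooled formula gives 33, the arcsine formula 36 and the continuity-corrected formula 41.

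**Step 2: power at 30 v 30, normal approximation.** The null standard error is √(0.525 × 0.475 × 2/30) = 0.1289. The alternative standard error is √(0.2275/30 + 0.21/30) = 0.1208. Power = Φ[(0.35 − 1.960 × 0.1289) / 0.1208] = Φ(0.81) = 79.0%.

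**Step 3: hold 30 Dsuvia patients and vary m.** The exact columns enumerate both binomial distributions. The last column is the standard error relative to 30 v 30, √[(1/30 + 1/m) / (2/30)], taking equal variances.

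| Comparators m | Normal approx. | Exact, uncorrected chi-square | Exact, Fisher | Relative SE |
|---|---|---|---|---|
| 13 | 56.7% | 59.6% | 53.4% | 1.29 |
| 20 | 69.1% | 71.5% | 67.3% | 1.12 |
| 30 | 79.0% | 79.8% | 71.4% | 1.00 |
| 40 | 84.4% | 84.8% | 79.6% | 0.94 |
| 45 | 86.2% | 86.6% | 81.9% | 0.91 |
| 55 | 88.9% | 89.1% | 86.8% | 0.88 |
| 60 | 89.8% | 90.0% | 88.1% | 0.87 |
| 90 | 93.2% | 92.9% | 90.2% | 0.82 |

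About 40 to 45 comparators reach 85% with the uncorrected chi-square test, and about 55 with Fisher. The standard error falls by 13% at 60 and by 18% at 90, so the gain flattens.

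**Step 4: the primary endpoint.** No SD is given for the opioid amount, so its power cannot be computed from the document. The factor 1/30 + 1/m applies approximately to the Wilcoxon comparison too, so the relative precision gain is similar.

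**Step 5: how many comparators to expect.** If a fraction f of all eligible patients in the window enrols, the expected number not enrolled when the 30th enrols is 30(1 − f)/f:

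- f = 33%: 60
- f = 40%: 45
- f = 50%: 30
- f = 60%: 20
- f = 70%: about 13

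Thirty or more are therefore expected only if f is 50% or less. Treating enrolment as independent between patients (negative binomial), the chance of at least 30 is 94% at f = 40%, 50% at 50%, 6% at 60% and 0.06% at 70%.

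**The case against.** **Both halves are conditional.** The document gives neither pool size nor uptake, and the pool cannot be both large and short. This stands. A reader might infer that the design cannot supply 30 comparators. The document does not support that: nothing shows uptake above one half, and eligible patients whom the pre-operative call missed, or who did not consent on the day, remain available as comparators.

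**The cap of 30 is inferred.** It comes from the per-group size together with random selection; no sentence says that exactly 30 will be drawn. The inference is reasonable, because taking everyone would need no selection, but it is an inference. Equal groups are also conventional in a pilot. Even so, this pilot states a power and a significance test.

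**The draw does not cause the power miss.** A reader might blame equal allocation for falling short of 85%. Step 1 shows that the sample-size calculation itself is low: 35 per group would be needed. Extra comparators compensate for that error.

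**The test matters.** A reader might take 40 comparators as enough. That is roughly true for the uncorrected chi-square test only; under Fisher, which the plan also permits, 40 give 79.6%.

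**Reaching back before the first Dsuvia patient is not a clean remedy.** The Informed Consent section describes standardising pain management during the study period and asking about Suboxone on the pre-operative call. Earlier patients might differ on both, and the concurrent window avoids that.

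**The list cannot be fixed without opening the intraoperative record.** Eligibility depends on intraoperative haemodynamic stability and on anaesthetic technique. A fixing rule must allow for this. The document also gives no evidence that a random draw would be manipulated, and eligibility judgements would be just as unblinded if all patients were taken.

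**Precision is not the main limitation.** More non-participants narrow the interval around a contrast that may be confounded. This stands in full.

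**Conclusion.** The point holds as a conditional design improvement. If more than 30 eligible non-Dsuvia patients exist in the window, a random 30 discards usable concurrent data. On the plan's sizing assumptions, going from 30 to 60 comparators raises exact power from 79.8% to 90.0% (uncorrected chi-square) or from 71.4% to 88.1% (Fisher), and cuts the standard error by about 13%. If more than half of all eligible patients enrol, fewer than 30 concurrent comparators are expected, and the plan has no rule for that case.

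The size of the effect rests on four things: reading the reduction as relative (70% to 35%), treating 30 as the comparator cap, assumed pool sizes and uptake, and rescue use as the sizing endpoint. The power figures do not carry over directly to the primary endpoint. The conclusion concerns precision and the handling of a shortfall; it does not show that the comparison is infeasible or that a larger comparison group would be less biased.

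**What to change.** In the Comparison group section, replace random selection with: all patients in the window who meet the criteria and did not receive Dsuvia, one operation per patient. State that eligibility is decided and the list fixed before opioid totals and PACU outcomes are abstracted. Because some criteria require the intraoperative record, eligibility should be a separate abstraction step limited to the fields that those criteria need.

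In the Statistical analysis section, keep 30 Dsuvia patients and restate power for 30 v the actual number of comparators, naming the test used.

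Add a shortfall rule: if fewer than 30 concurrent comparators are found, report the reduced power, and use any pre-study comparators only in a flagged sensitivity analysis.

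The cost is a short protocol change, extra chart abstraction by existing staff, and access to more records under the waiver. No extra enrolment, study drug or individual consent is needed. The report should say that the larger comparison group improves precision and leaves confounding between participants and non-participants unaddressed.

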The safety and efficacy of sufentanil have been demonstrated in different types of surgeries. After hip or knee arthroplasty, patients who received sublingual sufentanil reported lesser postoperative pain compared to placebo.¹⁴ Similar results were reported by patients who had undergone open abdominal surgery.¹⁵ Additionally, in one of the recent publications, the use of sublingual sufentanil in the preoperative period resulted in reduced opioid usage in the post-operative period and shorter time in the postoperative anesthesia care unit.¹⁶

In this case, series, we are testing the hypothesis that sublingual sufentanil (Dsuvia) will improve postoperative pain management in the PACU in ambulatory surgery patients taking Suboxone.

Primary Endpoint – We will evaluate the total amount of morphine equivalence (MME) in the perioperative period (defined as combined total opioid used intra-op and in the PACU).

Secondary Endpoint(s) – We will evaluate the time to fit to discharge from the PACU, the need for additional opioids and time to take the first additional opioid within 24 hours after being discharged from the hospital, and finally, the adverse events in the intraoperative period , PACU and in the 24 hours after being discharged from the PACU (i.e., nausea, vomiting, itching, hypotension, dizziness.)

Methods

Study Design:

Prospective case series study.

Inclusion criteria

- Age range 18-100 years
- Currently taking Suboxone
- ASA physical score 1-3
- Able to provide a signed informed consent
- General anesthesia (either endotracheal intubation or laryngeal mask airway) or **MAC** (**monitored anesthesia care**) without the use of regional anesthesia

Exclusion criteria

- Known allergic reactions to Dsuvia and its excipients
- Severe respiratory illness including exacerbation of asthma attack
- Significant intraoperative hemodynamic instability
- Use of Regional anesthesia techniques

Informed Consent

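### The plan does not require the same data source in both groups for in-hospital adverse events, so their planned comparison may partly measure how fully events were captured.

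*Combined protocol and SAP*

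**What the plan says.** The treated group is described under Study Design as a "Prospective case series study". Study Objective Assessments gives its data sources: "A research associate will be collecting the data prospectively and from the medical records". The sentence that follows adds "All the assessments will be coordinated with the standard of care administered at our hospital". No endpoint is assigned to one source or the other.

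The Comparison group section, which also requests a waiver of consent, has a single mode of collection: "For the comparison group, all the data points will be collected retrospectively". It adds "For comparison, group data points after the discharge from the hospital will not be collected", so the groups can be compared only on what happens before discharge.

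Two secondary endpoints fall in that window. One is discharge readiness ("We will evaluate the time to fit to discharge from the PACU"). The other is "the adverse events in the intraoperative period , PACU and in the 24 hours after being discharged from the PACU", with nausea, vomiting, itching, hypotension and dizziness as the listed examples.

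Statistical analysis plans that "categorical variables such as adverse events and the number of patients requiring additional opioids will be analyzed using chi-square analysis or Fisher's exact tests", two-sided at 0.05. It ties the Wilcoxon test to the primary endpoint and names no test for time to fit to discharge. The plan does not call for a common source, a common definition, a shared abstraction form, blinded abstraction or a chart-only sensitivity analysis.

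**The concern.** Three of the five listed adverse events (nausea, itching, dizziness) are symptoms that someone has to ask about or the patient has to volunteer. A research associate present during the stay can record symptoms that routine staff would not chart. For a comparison patient identified afterwards, a symptom exists in the data only if it was charted at the time.

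Group membership would then be fully aligned with the method of collection, and no analysis of the resulting data could separate a drug effect from a detection effect. Equal true rates could appear as an excess on Dsuvia. What is at stake is the pilot's comparative safety information. The missing post-discharge data are a separate matter: this point concerns the one window in which both groups have data.

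**Working it through.** **Sources side by side**

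| | Dsuvia group | Comparison group |
|---|---|---|
| In-hospital collection | Prospective and medical records, not assigned by endpoint | Retrospective only |
| After discharge | 24-hour call | None |
| Adverse events | Chi-square or Fisher | Same test |
| Time to fit to discharge | No test named | No test named |

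That comparison data come from charts is an inference from retrospective collection under a consent waiver, but no other realistic source is described.

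**Inputs for the size of the effect**

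- From Statistical analysis: n = 30 per group, two-sided 0.05, chi-square or Fisher. The plan gives no rule for choosing between the tests. The 30 is taken as given.
- Assumed, because the documents give no figures: a true event rate π that is equal in both groups, complete capture in the Dsuvia group, and a fraction c of events captured in the comparison charts.

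**Formula.** The observed rates are π (Dsuvia) and cπ (comparison). The false-positive rate is found by exact enumeration:

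P(reject) = Σₐ Σ_b Bin(a; 30, π) · Bin(b; 30, cπ) · 1[p(a, b) < 0.05],

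where a and b run from 0 to 30 and p(a, b) is the p-value of the uncorrected chi-square or Fisher's exact test.

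**Results**

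| True rate π | Capture c | Observed rates | Chi-square | Fisher |
|---|---|---|---|---|
| 40% | 50% | 40% v 20% | 0.392 | 0.298 |
| 30% | 50% | 30% v 15% | 0.281 | 0.192 |
| 20% | 50% | 20% v 10% | 0.194 | 0.096 |
| 10% | 50% | 10% v 5% | 0.106 | 0.019 |
| 5% | 50% | 5% v 2.5% | 0.031 | 0.002 |
| 30% | 70% | 30% v 21% | 0.123 | 0.076 |
| 20% | 70% | 20% v 14% | 0.094 | 0.044 |
| 30% | 100% | 30% v 30% | 0.049 | 0.026 |

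The last row is the reference: with equal capture the tests hold their level.

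**Imperfect capture in both groups.** Over true rates of 20% to 50%, 95% v 70% capture gives 0.082 to 0.164 (chi-square) or 0.036 to 0.107 (Fisher). With 95% v 50% capture the ranges are 0.170 to 0.438 and 0.078 to 0.340. The conclusion does not depend on complete capture in the Dsuvia group.

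**Discharge readiness.** No calculation is possible. The documents do not say which time is recorded as fit for discharge in either group.

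**The case against.** The strongest reply is that the plan does not say the in-hospital endpoints are collected differently. Medical records are one of the two stated sources for the Dsuvia group, assessments are tied to routine care, and the only collection that is plainly research-specific is the 24-hour call, which has no counterpart in the comparison group. In-hospital events could therefore come from the same routine record in both groups. This stands as far as it goes: a mismatch is permitted by the plan, not established. Equally, nothing in the plan prevents one.

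The size rests on assumptions, and this also stands. The only event rate in the documents is the figure of under 2% for common adverse events in Human Safety. It comes from a different population and is not a forecast, but if rates here were 5% or lower there would be no inflation. At 10% only the chi-square test is affected, and Fisher is the natural choice with sparse counts. Vomiting and hypotension are plausibly better charted than the three symptoms, so the scenarios do not apply equally to every event.

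The endpoints are secondary, in a pilot that states it is not powered for them. That limits the consequence, but low power does not protect against biased capture.

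A reader might also infer that readiness would be noted promptly on Dsuvia while charts hold only the later departure time, so that Dsuvia would look faster and the two biases would run in opposite directions. The documents do not support this. They do not say how readiness is recorded in either group, and discharge of the enrolled patients follows institutional criteria, which may leave a comparable charted time.

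**Conclusion.** The concern holds in a limited form. As written, the plan permits fuller capture of patient-reported events in the Dsuvia group and then tests the groups as if they had been measured alike. If charts hold half of events and true rates are 20% to 40%, a false significant difference arises in about 19% to 39% of trials by chi-square or 10% to 30% by Fisher. With 70% captured, at true rates of 20% to 30%, the figures are about 9% to 12% and 4% to 8%. All of these rest on assumed event and capture rates.

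For time to fit to discharge, the finding is only that the source and the time point are unspecified. A reader might conclude that neither secondary endpoint can be answered without bias; that is too strong, because a common source is possible under the plan as it stands. The primary endpoint is not part of this point: opioid doses are probably in the medication record for both groups, though that too is an inference. The change should be made, but it is not critical to the primary analysis.

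**What to change.** State in Comparison group and Statistical analysis that, for every between-group comparison of in-hospital adverse events and of time to fit to discharge, both groups will be abstracted from the same chart sources with one shared form. Define on that form what counts as each event, and which charted time point represents readiness. Report prospectively collected events and the 24-hour call for the Dsuvia group descriptively only.

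The cost is some wording and one abstraction form, since the Dsuvia patients' records are already a data source. Enrolment, follow-up and sample size do not change, and full safety capture in the Dsuvia group is kept.

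There are two downsides. The compared event rates will be lower than the fully collected ones. Staff may also chart more for patients they know to be in a study, so the bias is reduced but not removed. If the sponsor prefers to keep its planned comparison, a prespecified chart-only sensitivity analysis beside it would be an acceptable alternative.

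### Adverse events are defined to 24 hours after PACU discharge and tested between groups, but comparator data stop at hospital discharge; the handling of dosed patients who meet the intraoperative-instability exclusion is also unstated

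*Combined protocol and SAP*

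**What the plan says.** All places are in the combined protocol and SAP.

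- **Secondary Endpoint(s).** Adverse events are assessed in the intraoperative period, "PACU and in the 24 hours after being discharged from the PACU (i.e., nausea, vomiting, itching, hypotension, dizziness". The same sentence lists "the need for additional opioids and time to take the first additional opioid within 24 hours after being discharged from the hospital".
- **Informed Consent** (follow-up text). A research associate "will call the patient 24 hours after discharge from the PACU to collect the information regarding their post-discharge opioid use". The call also covers adverse events. It is described only for enrolled patients.
- **Comparison group.** "For the comparison group, all the data points will be collected retrospectively", and "For comparison, group data points after the discharge from the hospital will not be collected".
- **Study Objective Assessments.** "A research associate will be collecting the data prospectively and from the medical records".
- **Statistical analysis.** "categorical variables such as adverse events and the number of patients requiring additional opioids will be analyzed using chi-square analysis" or Fisher's exact test. No time window is attached to either variable. All tests are two-sided at 0.05, and secondary outcomes are stated to be unpowered.
- **Primary Endpoint.** Perioperative morphine equivalents, "defined as combined total opioid used intra-op and in the PACU".
- **Exclusion criteria, Informed Consent and the Dsuvia medication schedule.** Marked hemodynamic instability during surgery is an exclusion. Screening is done before the day of surgery, and the first Dsuvia dose falls between induction and incision. Comparators are sampled from patients who already meet all criteria.

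**The concern.** The endpoint definition, the data collection and the test do not fit together. The definition includes a period that is observed in one group only, and the analysis section does not restrict the test to the period observed in both. If each patient were classified as having an event or not over the full window, Dsuvia patients would have an extra 24 hours in which to become a case. That would bias the comparison towards apparent harm from Dsuvia and could hide a real in-hospital reduction.

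Three related gaps sit beside this one.

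- Even inside the hospital, ascertainment differs: prospective collection plus records for Dsuvia, retrospective collection for comparators. Events such as itching or dizziness may be noted by a research associate and never charted.
- The endpoint list uses additional opioids for the post-discharge period, while the analysis section tests the number of patients requiring them. The post-discharge version has no comparator data.
- The instability exclusion can be met after a patient has been dosed, and no analysis population is defined. Hypotension is itself a listed adverse event. Removing dosed patients for instability would therefore delete outcomes and make the primary comparison conditional on something that happened after dosing.

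**Working it through.** **No plan figure bears on this point.** The only computable design figure is 30 per group. For 70% versus 35%, two-sided 0.05 and 85% power, the standard pooled formula gives 35 per group. That is a separate matter, and nothing below depends on it. I take 30 per group as planned.

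**What each group can supply**

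| Period | Dsuvia | Comparison |
|---|---|---|
| Intraoperative and PACU | prospective plus records | retrospective |
| 24 h after discharge | telephone call | not collected |

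Only the first row supports a between-group test.

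**Size if the full window were tested**

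Inputs: n = 30 per group and two-sided 0.05 (Statistical analysis). The in-hospital rate b and post-discharge rate r are my assumptions, because the documents give neither by window. In-hospital and post-discharge events are taken as independent.

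- Comparator observed rate = b.
- Dsuvia observed rate = 1 − (1 − b)(1 − r).
- Rejection probability = the sum, over all pairs of counts, of Bin(x; 30, Dsuvia rate) × Bin(y; 30, comparator rate) for pairs with p < 0.05. The chi-square test is uncorrected.

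With b = 20% in both groups, so no true in-hospital difference:

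| r | Dsuvia rate | Extra Dsuvia patients with an event | Chi-square | Fisher |
|---|---|---|---|---|
| 0 (equal windows) | 20% | 0 | 4.9% | 2.2% |
| 2% | 1 − 0.80 × 0.98 = 21.6% | 30 × 0.016 = 0.48 | 5.1% | 2.4% |
| 10% | 1 − 0.80 × 0.90 = 28% | 30 × 0.08 = 2.4 | 10.9% | 6.5% |
| 20% | 1 − 0.80 × 0.80 = 36% | 30 × 0.16 = 4.8 | 27.9% | 19.8% |

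At r = 10%, 10.6 of the 10.9 chi-square points are rejections towards harm from Dsuvia. Over b and r each from 10% to 30%, false rejection ranges from 8.5% to 72.0% (chi-square) and from 5.1% to 61.2% (Fisher). With 2% in both windows it is 1.7% and 0.06%.

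The same shift can mask benefit. Suppose Dsuvia truly lowered the in-hospital rate from 40% to 20%, a scenario the plan does not hypothesize. The chance of showing it would fall from 39.2%/29.8% (chi-square/Fisher) in a common window to 15.8%/10.5% with 10% post-discharge events added.

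**Order of events for the exclusion.** Screening comes first, then induction, first dose, incision and the rest of surgery. Instability can arise between induction and dosing or at any time after dosing. Only the first of these precedes exposure, and the criterion does not distinguish them.

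**The case against.** The strongest reply is that the plan never describes a pooled test. The endpoint sentence lists three periods and defines no any-event composite, and the Comparison group section is open about the missing follow-up. Read together, an in-hospital comparison is the only feasible one, and it has no window bias. This largely stands. A reader might infer that the plan prescribes a biased test, and the documents do not support that. What remains is that the only stated definition includes the 24 hours and the test names no window, so the choice is left open until data are in hand.

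A reader might also infer that the test of additional opioids cannot be done. That goes too far. The sample size rests on rescue opioid in the PACU, and the interim text under Data Management also refers to extra opioid doses there, so PACU use is the likely meaning. Some ambiguity stays because the endpoint list uses the phrase for the time after discharge. For those post-discharge endpoints, an evaluation in one group is compatible with the wording.

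On size, every rate above is assumed. The one adverse-event figure in the documents, under 2% in the Human Safety section, would make the effect negligible. It is tied neither to a post-discharge window nor to Suboxone patients, so it does not settle the matter.

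Finally, a reader might infer that dosed patients will be dropped for instability. The text neither requires nor excludes this, and the criterion could be applied between induction and dosing. Neither the frequency nor the direction of any effect can be derived from the documents.

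**Conclusion.** The point holds in a limited form. The adverse-event endpoint, as defined, extends into a period with data from the Dsuvia group only, and the between-group test is not confined to the shared period. Used over the full window, it would count post-discharge events against Dsuvia alone. The difference in in-hospital ascertainment is a second asymmetry, and it would remain even with matched windows.

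The consequence is confined to secondary, unpowered outcomes of a pilot. It does not reach the primary endpoint, which ends in the PACU. The size is unknown: negligible at an assumed 2% post-discharge rate, and material at 10% or more, given an assumed 20% in-hospital rate, independence and 30 per group.

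The instability exclusion is a separate gap in wording. It is the only part that could touch the primary comparison, and only if dosed patients were in fact removed.

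**What to change.** 1. In Statistical analysis, limit between-group tests of adverse events and additional opioids to the intraoperative-plus-PACU window. Use the same definitions and record-documented events in both groups for the main test, and report prospectively observed Dsuvia events separately. This reduces the ascertainment difference but may not remove it, since study staff's observations can reach the chart.
2. Report post-discharge adverse events, opioid need and time to first opioid for the Dsuvia group only, with 95% confidence intervals and no p-value. As a guide to precision, 6/30 = 20% has an exact interval of 8% to 39%, and 0/30 has 0% to 12%.
3. Keep every patient given at least one Dsuvia dose in the efficacy and safety analyses, and count instability after dosing as an outcome. Apply the exclusion in both groups only up to a common time point recorded in both, such as the end of induction. Incision would not serve: it follows dosing, so instability between dose and incision would be an outcome in one group and an exclusion in the other.
4. Reconcile the Exclusion criteria, the screening text under Informed Consent and the dosing schedule on when the criterion is assessed. The clinical criterion itself is for the investigators.

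The cost is a few sentences in the statistics section, a stated assessment time, separate tabulation of charted and observed Dsuvia events, and a change to the comparator sampling frame in the Comparison group section. No new follow-up is needed. The downsides are that no comparative claim can be made after discharge, record-based counts may miss some events in both groups, and a few hemodynamically complicated patients will be included.
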